#### **6.4.3. Number of Nighttime Awakenings Due to Asthma During Treatment Period**

Patients will record nighttime awakenings due to asthma in the e-diary daily. Sites will check the records of nighttime awakenings during the all study visits (screening and run-in), treatment period and follow-up visit.

Monthly analysis windows during the treatment period will be derived for each patient using algorithm detailed in Section 6.1.1. The monthly number of nighttime awakenings due to asthma during the treatment period will be calculated and normalized to 28 using the formula below.

$$\frac{\sum \text{days nighttime awakenings during an analysis window}}{\text{Days with assessments recorded in the eDiary during an analysis window}} \times 28$$

The baseline will be calculated based on the data from 7 days preceding day of randomization and be normalized to 28 days similarly.

The change from baseline in the monthly numbers of nighttime awakenings due to asthma during treatment period will be analyzed using MMRM in a manner analogous to the analysis as described in Section 6.3.2. Baseline monthly number of nighttime awakenings due to asthma will be included in the analysis model.

In additional, weekly analysis windows (weeks 1 to 8) will be derived for each patient using algorithm detailed in Section 6.1.1. The weekly number of nighttime awakenings due to asthma during weeks 1 to 8 will be calculated using the formula below:

$$\frac{\sum \text{days nighttime awakenings during an analysis window}}{\text{Days with assessments recorded in the eDiary during an analysis window}} \times 7$$

The baseline will be calculated based on the data from 7 days preceding day of randomization similarly. The change from baseline in the weekly numbers of nighttime awakenings due to asthma during weeks 1 to 8 will be analyzed using MMRM similarly. Per the ICE handling strategy, for patients who did not complete the treatment period, observations after the end of the treatment period will be discarded and treated as missing observations.

#### 6.4.4. Percent Decrease in ICS Dose During Treatment Period

Inhaled corticosteroid (ICS) use will be recorded as one of asthma medications in the prior and concomitant medication data on the CRF.

Monthly analysis windows during the treatment period will be derived for each patient using algorithm detailed in Section 6.1.1. The monthly ICS usage in an analysis window will be the summation of reported usages in the analysis window.

The baseline will be the summation of reported usage from 28 days preceding day of randomization.

The percent decrease in ICS usage in an analysis window will be calculated using the formula below:

$$\frac{\text{baseline value} - \text{postbaseline value}}{\text{baseline value}} \times 100\%$$

The percent decreases and changes from baseline in monthly ICS usage during the treatment period will be analyzed using MMRM in a manner analogous to the analysis as described in Section 6.3.2. Baseline daily ICS usage will be used in the analysis model.

In additional, weekly analysis windows (weeks 1 to 8) will be derived for each patient using algorithm detailed in Section 6.1.1. The weekly ICS usage in each weekly analysis window will be the summation of reported usages in the analysis window. The baseline will be the summation

of reported usage from 7 days preceding day of randomization. The percent decrease in ICS usage in a weekly analysis window will be calculated similarly using formulas above. The percent decreases and changes from baseline in monthly ICS usage during weeks 1 to 8 will be analyzed using MMRM similarly. Per the ICE handling strategy, for patients who did not complete the treatment period, observations after the end of the treatment period will be discarded and treated as missing observations.

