- TEV-48574 [REDACTED]
- Placebo to match TEV-48574

With randomization, patients enter the 16-week treatment period. The patients will receive the IMP loading dose on the day of randomization and the subsequent corresponding IMP maintenance dose every 2 weeks for a total of 8 doses (1 loading dose and 7 maintenance doses).

Patients qualifying for randomization will continue the same background asthma controller regimen as used during run-in without change for the first 4 weeks of the treatment period; this regimen includes study-provided controller inhalers (ICS+LABA and additional ICS), plus any additional controller medications that met the eligibility criteria. After week 4, background asthma controller therapies will be decreased in a structured manner in patients not experiencing LoAC (see Section 6.1.1 for LoAC definition) (the patient will be aware of the dose decreases). The first step is implemented after the first 4 weeks of the treatment period and includes discontinuing LABA and any additional asthma controller medications, with the exception of study-provided additional ICS. The second step will be made 2 weeks later. The second and subsequent steps will consist of decreasing the ICS dose step-wise weekly, by ~50%. For patients on ICS doses greater than the high dose ICS+LABA twice a day, the total ICS dose should also be decreased step-wise weekly, by ~50%. Excluding patients who meet LoAC criteria during the structured withdrawal of background asthma controller therapies, the duration of treatment with IMP only will be approximately 8 or 9 weeks. Since study-provided asthma controller formulations may vary locally, Table 1 shows an example of the step-wise structured withdrawal. Eligibility assessment for structured withdrawal of background asthma controller therapies (between scheduled in-person visits) may be done by phone; if it is suspected that a patient meets the criteria for LoAC, the investigator may ask the patient to attend the site for an unscheduled visit.

Table 1: Examples of Schedule of Withdrawal of Background Asthma Controller Therapies

Time point: Weeks after randomization (visit number)	Action	Dose at start of treatment period	
		Fluticasone/salmeterol 500/50 µg BID	Fluticasone/salmeterol 250/50 µg BID
4 weeks (V3)	Discontinue LABA and other non-ICS asthma controllers*	FP 500 BID	FP 250 BID
6 weeks (V4)	First ICS decrease	500 decreased to 250 BID	250 decreased to 100 BID

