7 weeks (Telephone, V5)	Second ICS decrease	250 decreased to 100 BID	100 BID decreased to 0
8 weeks (V6)	Third ICS decrease	100 BID decreased to 0	0

*Other asthma controllers (eg, LAMA, leukotriene antagonists) will also be discontinued.

Note: Last IMP administration 14 weeks after randomization (visit 9); end-of-treatment visit (EOT) 16 weeks after randomization

BID=twice daily; FP=fluticasone propionate; ICS=inhaled corticosteroids; LABA=long-acting beta-agonists; LAMA= long-acting muscarinic antagonist; V = visit.

Patients will be monitored for worsening of asthma and potential LoAC (and CAE) both at scheduled visits and in between visits via hand-held spirometry and e-diary. Asthma specific alerts will be sent for the following:

- Decrease in morning FEV₁ $\geq 20\%$ from baseline on 2 consecutive days OR decrease in morning PEF $\geq 30\%$ from baseline on 2 consecutive days
- Increase in rescue medication use/SABA of 4 or more puffs over baseline for 2 or more consecutive days OR ≥ 12 puffs in any single day
- Increase of 2 nighttime awakenings due to asthma over baseline on 2 consecutive days

In the event of an alert, the site will follow-up with the patient. An alert does not mean that the patient's medications need to be changed or that study drug should be discontinued, only that the patient should be contacted and evaluated by phone or at an unscheduled visit according to investigator judgment. If, in the investigator's judgment, LoAC is suspected, every effort to have the patient evaluated at an unscheduled visit should be made.

Definitions of LoAC and Clinical Asthma Exacerbation (CAE) are presented in Section 6.1.1 and Section 6.1.2. LoAC events and CAEs will be treated by the investigator according to local standard of care. In the event of a LoAC or CAE, IMP will be discontinued and background asthma controller therapy will be restarted or increased per investigator judgment. Patients who experience LoAC or CAE will remain in the study for assessments. (Note: CAEs are a subset of LoAC events; see Section 6.1.1 and Section 6.1.2 for definitions).

Study procedures and assessments are described in detail Section 3.6.

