6.1.1. Loss of Asthma Control (Primary Efficacy Endpoint)

The primary efficacy endpoint is the proportion of patients who experience LoAC during the treatment period.

LoAC is defined as any one of the following during the treatment period:

- Morning PEF decrease $\geq 30\%$ from baseline on 2 consecutive days or morning handheld FEV₁ decrease $\geq 20\%$ from baseline on 2 consecutive days
- Increase in SABA/quick-relief medication ≥ 6 puffs over baseline use in 24 hours on 2 consecutive days*
- Increase in ICS dose $\geq 4x$ most recent dose*
- Systemic corticosteroid use
- Asthma ER visit or hospitalization

A patient who meets criteria for LoAC will discontinue IMP, and resume or increase background asthma controller therapies, but will remain in the study. LoAC events will be treated by the investigator according to local standard of care. An effort should be made to collect blood samples for TEV-48574 serum concentration and ADA testing at (or as close to) the time of LoAC as possible in addition to the scheduled assessments (see [Table 3](#) [treatment period] and [Table 4](#) [follow-up]).

In addition to the primary efficacy endpoint of the proportion of patients who experience LoAC, time to LoAC will be a key secondary endpoint (see Section 9.5.2).

*Once background asthma controller therapy has been standardized per protocol, the asthma controller regimen is to remain stable throughout the treatment period until the structured withdrawal per protocol or treatment of LoAC/CAE (Section 6.1.2). Patients who experience LoAC, including CAEs, during the treatment period will discontinue IMP and resume/increase background asthma controller therapy for the remainder of the study.

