#### 1.7. Estimand for Primary Efficacy Endpoint

An estimand, in general, includes 5 inter-related attributes – treatment condition, population of interest, variable (endpoint) of interest, intercurrent events (ICE) along with the strategy for handling ICE, and population-level summary for the endpoint. The four attributes of the estimand are defined as follows:

**Treatment condition:** TEV-48574 [REDACTED] vs. placebo administered bi-weekly in patients on stable background inhaled corticosteroids (ICS) / long-acting beta2 agonist (LABA) in the first four weeks but with background asthma controllers withdrawn in a structured manner from week 4 to week 8.

**Population:** The patients with T2-low and non-T2 uncontrolled severe asthma met all inclusion criteria and met none of the exclusion criteria.

The intent-to-treat (ITT) analysis set as defined in Section 3.1 will be the primary analysis set for efficacy. In the data analyses, the treatment will be assigned based on the treatment to which patients were randomized, regardless of which treatment they actually received.

**Variable:** The proportion of patients who experience LoAC during the 16-week treatment period due to the initially randomized treatment as actually taken (Mallinckrodt, 2013).

**Intercurrent events:** Early treatment discontinuation will result in a lack of exposure to the initially randomized treatment and the patient being put on alternative medications. Observations after IMP discontinuations may not reflect the treatment effects of the initially randomized

treatment. In addition, an early discontinuation prior to week 16 without LoAC will result in a missing observation of the primary efficacy endpoint altogether.

As the strategy to handle the ICEs for the primary analysis, each patient's treatment period is defined as from the first dose to the last dose + 14 days. Patients who withdraw from the study prior to week 16 without LoAC or early terminated the study treatment without experiencing LoAC during the patient's treatment period will be analyzed as having experienced LoAC, if the assessed reason of discontinuation is lack of efficacy or due to an asthma-related adverse event. Patients who withdraw from the study without LoAC or early terminated treatments without experiencing LoAC during the patient's treatment period for other reasons will be analyzed as having not experienced LoAC.

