### **3. ANALYSIS SETS**

#### **3.1. Intent-to-Treat Analysis Set**

The intent-to-treat (ITT) analysis set will include all randomized patients and will be used as the population for the primary efficacy analysis.

In the ITT analysis set, treatment will be assigned based on the treatment to which patients were randomized, regardless of which treatment they actually received.

Data collected from patients after treatment discontinuation will be included in the ITT analysis set.

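### The ICS-decrease analysis discards most of the ICS use that follows LoAC, so it mainly describes the mandated taper and strongly attenuates any treatment difference

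*SAP*

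**What the plan says.** **Endpoint.** SAP 6.4.4 adds up the ICS use recorded in each monthly window, compares it with the sum over the 28 days before randomization, and models percent decrease and change with an MMRM patterned on SAP 6.3.2. Citing the intercurrent-event strategy, it says that for patients who do not complete the treatment period "observations after the end of the treatment period will be discarded and treated as missing observations". SAP 6.3.2 carries the same rule.

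**Cut-off.** SAP 1.7 sets a per-patient limit: the "treatment period is defined as from the first dose to the last dose + 14 days". It describes the intercurrent event as early treatment discontinuation with a move to other medication.

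**Analysis set.** SAP 6.4 places the endpoint on the ITT set, and SAP 3.1 says: "Data collected from patients after treatment discontinuation will be included in the ITT analysis set".

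**ICS without LoAC.** Protocol 3.1 imposes a taper: "The second and subsequent steps will consist of decreasing the ICS dose step-wise weekly, by ~50" per cent. In Table 1 the higher example starts with "500 decreased to 250 BID" at week 6 and ends with "100 BID decreased to 0" at week 8; the lower example reaches zero at week 7. Patients entering on higher doses finish later (Protocol 3.6.1.2.8).

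**ICS with LoAC.** Outside LoAC or CAE treatment, Protocol 6.1.1 says the "asthma controller regimen is to remain stable throughout the treatment period until the structured withdrawal per protocol". At LoAC: "A patient who meets criteria for LoAC will discontinue IMP, and resume or increase background asthma controller therapies, but will remain in the study".

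**Windows.** SAP 6.1.1 begins and ends the monthly windows at actual IMP administrations.

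**The concern.** A treatment effect on ICS dose needs room for the dose to differ between arms. Among patients without LoAC there is almost none, because the protocol dictates the same steps whatever the assigned treatment. Non-adherence and dropout aside, the arms can separate only through patients who lose control and go back on ICS.

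Those patients are the ones whose later ICS records are set to missing. The records exist, since the patients stay in the study and ICS is captured as concomitant medication. The MMRM then treats the gaps as missing at random and fills them, in effect, largely from patients still on the taper, although the gaps arise from the very event that raises ICS use.

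At stake is the reading of a listed secondary endpoint: a near-null result would largely be produced by the rule, yet could be reported as no steroid-sparing effect.

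**Working it through.** The documents give no effect size or power for this endpoint. The design inputs are LoAC rates of 27% and 10.8% and 62 patients per arm (Protocol 9.1). The 62 reproduces: a chi-square test at one-sided 0.1 with 80% power needs 52 per arm, and 52/0.85 = 61.2, rounded up to 62.

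**Percent decrease fixed by the taper (Table 1, no LoAC)**
- 500 BID start (1000 per day), month 2: 14 days at 1000, 7 at 500, 7 at 200 = 18,900; 1 - 18,900/28,000 = 32.5%.
- 250 BID start (500 per day), month 2: 14 days at 500, 7 at 200, 7 at 0 = 8,400; 1 - 8,400/14,000 = 40%.
- Month 1 is 0% and months 3 and 4 are 100% for both. The values are the same in both arms.

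**Assumptions not in the documents.** LoAC day uniform over days 1-112, 29-112 or 57-112; ICS returns to the baseline dose on the LoAC day; no other dropout; full adherence; doses on days 1, 15, ..., 99, with none given on the day of LoAC. Retention runs for 14 days counted from the dosing day. Month 4 is days 85-112. Differences are between observed-window means, not fitted MMRM estimates.

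**All data to week 16, month 4.** A patient with LoAC on day t shows 0% decrease if t ≤ 85 and (t - 85)/28 if later. Summed over days 86-112 this is (1 + ... + 27)/28 = 13.5. With D possible LoAC days (112, 84 or 56), the mean shortfall from 100% is 100 × (1 - 13.5/D), and the arm difference is (0.27 - 0.108) × that shortfall:
- D = 112: 0.162 × 87.9 = 14.2
- D = 84: 0.162 × 83.9 = 13.6
- D = 56: 0.162 × 75.9 = 12.3

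**SAP rule, month 4.** Patients with LoAC by day 85 have no month-4 value. For LoAC on days 86-98 the retained resumed days run 13 down to 1, on day 99 they are 0, and on days 100-112 they are again 13 down to 1: a total of 91 + 91 = 182.
- Raw sums, as the SAP specifies: mean shortfall (182/27)/28 = 24.1%.
- Per day observed (14 days, then 28): (91/14 + 91/28)/27 = 36.1%.
- Share of an arm's retained patients who had LoAC, with p the arm's LoAC rate: (27p/D) / (1 - p + 27p/D). For D = 56 this is 0.1302/0.8602 = 15.1% (placebo) and 0.0521/0.9441 = 5.5% (active). The raw-sum difference is (0.1513 - 0.0552) × 24.1 = 2.3. The other rows follow in the same way.

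| LoAC days | All data | SAP rule, raw sums | SAP rule, per day |
|---|---|---|---|
| 1-112 | 14.2 | 1.3 | 1.9 |
| 29-112 | 13.6 | 1.7 | 2.5 |
| 57-112 | 12.3 | 2.3 | 3.5 |

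A simulation under the same assumptions agrees within about 0.1 point. With 62 per arm and a Welch t-test at two-sided 0.05, month-4 power is about 0.59-0.61 with all data and about 0.10-0.28 under the SAP rule.

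**Raw-sum artefact.** If 14 days at an unchanged dose are retained and set against a 28-day baseline, the result reads as 1 - 14/28 = 50% decrease. With LoAC possible from day 1, days 1-15 leave 14 retained days, so month 1 shows 0.27 × (15/112) × 50 = 1.8% for placebo and 0.108 × (15/112) × 50 = 0.7% for active. That is about 1 point in favour of the arm with more early LoAC, although no dose was reduced.

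**The case against.** **Scope.** The rule covers patients who did not complete the treatment period. LoAC patients remain in the study, Protocol 4.4.1 keeps LoAC stops apart from other IMP discontinuations, SAP 2.1 ends the treatment period at week 16, and SAP 1.7 introduces the per-patient period for the primary analysis. One could argue that LoAC patients are exempt. But SAP 6.4.4 invokes the intercurrent-event strategy, and the event described in SAP 1.7, treatment stopped early and replaced by other medication, is what happens at LoAC. Nothing exempts LoAC patients. If exemption was intended, the SAP must say so.

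**Estimand choice.** Restricting to on-treatment data is a declared, repeated choice, and ICS after LoAC reflects local care off IMP. That is arguable for FEV1 or ACQ-6. Here the on-treatment quantity is mostly the protocol's own taper, so this is more than a preference between estimands.

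**SAP 3.1.** A general analysis-set statement can yield to a specific endpoint rule. That stands in part: the two texts sit poorly together and need reconciling, but this alone would not carry the point.

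**Low stakes.** The all-data contrast largely restates the LoAC difference, which the primary endpoint already tests; this endpoint is other-secondary and hypothesis-generating. That stands and limits the weight of the point.

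**Restart dose.** The dose is left to investigator judgment (Protocol 3.1), so the sizes above are conditional. That also stands.

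**Conclusion.** The endpoint as planned mainly describes the taper. At the design LoAC rates and under the stated assumptions, the month-4 difference falls from about 12-14 points to about 1-4. The sizes depend on LoAC timing and on the assumed return to the baseline dose; the direction follows from the design.

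A reader might infer that the endpoint cannot show a treatment effect at all, or that only patients on the taper remain. The documents do not support that. The cut is last dose + 14 days, not the day IMP stops, so up to about two weeks of resumed ICS is kept and a small difference survives; it would be exactly zero only if data ended at LoAC. Nor is the loss the full 27 - 10.8 = 16.2 points: that is a ceiling requiring every LoAC to precede month 4. The primary analysis and sample size are untouched.

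**What to change.** For this endpoint, amend SAP 6.4.4 to:

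1. Analyse all recorded ICS use to week 16, regardless of IMP discontinuation or LoAC, and delete the discard sentence. This also settles the tension with SAP 3.1 here.
2. State that the discard rule in SAP 6.3.2 does not apply. Otherwise the monthly MMRM, defined by analogy to that section, still inherits it.
3. Define the monthly windows by study day. The later windows in SAP 6.1.1 hang on IMP administrations that never occur once IMP is stopped, so they are undefined for the patients being brought back in.
4. Express ICS use per day observed, at baseline and afterwards, instead of a raw sum against 28 days. SAP 6.4.3 already normalizes awakenings by days recorded.

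If the sponsor prefers to keep the on-treatment version, it should be labelled descriptive, with a note that it reflects the taper. The cost is SAP wording and programming: no new data, visits or clinical rules.

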#### **6.4.5. Other Lung Function Parameters as Assessed by Hand-Held Spirometry at End of Treatment and Throughout the Study**

Spirometry will be performed both at the site and by hand-held spirometer.

On-site spirometry will include full-flow volume loops (FVC, FEV1, FEV1/FVC, FEF25%-75% and PEF) and reversibility testing at visit 1 (DoR), visit 3, visit 6, visit 8, and visit 10 during the treatment period. Changes from baseline in these parameters at EOT and throughout the study will be analyzed in a manner analogous to the analysis as for FEV1 described in Section 6.3.3.

Hand-held spirometry (FEV1, PEF) will be performed daily. Monthly analysis windows during the treatment period and post-treatment (follow-up period) will be derived for each patient using algorithm detailed in Section 6.1.1. The monthly average of FEV1 and PEF during each analysis window will be calculated using the formula below:

$$\frac{\sum \text{an efficacy variable during an analysis window}}{\text{Number of Days in the analysis window}}$$

The baseline will be calculated based on the data from 28 days preceding day of randomization similarly.

The change from baseline in the monthly averages of hand-held spirometry FEV1 and PEF values at EOT will be analysis using ANCOVA in a manner analogous to the analysis as described in Section 6.3.2. For patients who did not complete the treatment period, the last analysis window during the treatment period will be used. For patients who are lost-to-follow-up (no ET assessment) prior completion of the treatment period, the last analysis window during the treatment period will be used for the analysis.

The changes from baseline in monthly averages of hand-held spirometry FEV1 and PEF values throughout study will be analyzed using analyzed using MMRM in a manner analogous to the analysis as described in Section 6.3.2. The corresponding baseline value will be included in the analysis models. Per the ICE handling strategy, for patients who did not complete the treatment period, observations after the end of the treatment period will be discarded and treated as missing observations.

In additional, weekly analysis windows (weeks 1 to 8) will be derived for each patient using algorithm detailed in Section 6.1.1. The weekly average of FEV1 and PEF during each analysis window will be calculated similarly using the formula above. The baseline will be the summation of reported usage from 7 days preceding day of randomization. The changes from baseline in weekly averages of hand-held spirometry FEV1 and PEF values during week 1 to 8 will be analyzed using analyzed using MMRM similarly.

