### **4.2. Specification of Baseline Values**

Unless otherwise noted, the baseline for clinic visit variables will be the last observed value before the first dose of study drug. The baseline for absolute eosinophil count will be the average of measurements prior to the administration of the first IMP.

The baseline for hand-held spirometry parameters and e-diary variables will be the average of the values over the 7 days preceding day of randomization.

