### **4.3. Handling Withdrawals and Missing Data**

For all safety variables, only the observed data from the patients will be used in the statistical analyses, ie, there is no plan to estimate missing data, unless otherwise specified.

Dates that have incomplete information (the month and year or just the year is available) will be estimated for the purpose of calculating variables that are dependent on time if necessary. Day will be estimated as the first day (01) of the month (if month and year of partial date are available) or middle (July 1) of the year (if only year is available), unless otherwise noted. The imputations for partial dates are only for calculation purpose. Original date variables will not be modified. Listings will list dates as collected.

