## 6. EFFICACY ANALYSIS

### 6.1. General

The ITT analysis set (Section 3.1) will be used for all efficacy analyses unless otherwise noted. Summaries will be presented by treatment group. The mITT and per-protocol analysis sets (Section 3.4) will be used as supplementary analysis for the primary analysis. All efficacy related data will be listed using ITT analysis set unless otherwise specified.

The baseline for clinic visit variables will be the last observed value before the first dose of study drug.

The baseline for spirometry parameters and e-diary variables will be based on the daily average of the values over the 7 days preceding day of randomization.

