#### 6.3.4. Use of SABA Quick Relief Medication at EOT and Throughout Study

The number of inhalations/puffs of SABA/quick-relief inhaler will be recorded in the e-diary daily. Study sites will monitor rescue medication use during the study visits screening and run-in visit, all visits during treatment period, and follow-up visit. Study sites are also responsible for responding to asthma specific alert criteria related to SABA/quick-relief inhaler use.

Analysis windows throughout the study for during the treatment period and post-treatment (follow-up period) will be derived for each patient using algorithm detailed in Section 6.1.1.

The daily average of the inhalations/puffs of SABA/quick-relief inhaler in each monthly analysis window will be calculated using formula below:

$$\frac{\sum \text{inhalations/puffs in an analysis window}}{\text{number of days in an analysis window}}$$

The baseline daily average of use of SABAs will be calculated based on the data from 7 days preceding day of randomization similarly.

The change from baseline in the daily average of the uses of SABA quick relief medication at EOT will be analysis using ANCOCA in a manner analogous to the analysis as described in Section 6.3.2. For patients who did not complete the treatment period, the last analysis window during the treatment period will be used. For patients who are lost-to-follow-up (no ET assessment) prior completion of the treatment period, the last analysis window during the treatment period will be used for the analysis.

The change from baseline in the daily average of the use of SABA quick relief medication throughout study will be analyzed using MMRM in a manner analogous to the analysis as described in Section 6.3.2. Per the ICE handling strategy, for patients who did not complete the treatment period, observations after the end of the treatment period will be discarded and treated as missing observations.

The baseline daily average of use of SABAs will be included in the analysis models.

In additional, weekly analysis windows (weeks 1 to 8) will be derived for each patient using algorithm detailed in Section 6.1.1. The daily average of the inhalations/puffs of SABA/quick-relief inhaler in each weekly analysis window will be calculated similarly using formula above. The change from baseline in the daily average of the use of SABA quick relief medication during weeks 1 to 8 will be analyzed using MMRM similarly.

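### SABA use and hand-held FEV1/PEF are averaged over all days in the window, so missed days count as zero, and SAP 6.4.5 uses baselines that contradict SAP 4.2 and 6.1

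*SAP*

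**What the plan says.** **Denominators.** SAP 6.3.4 divides the puffs summed over a window by the "number of days in an analysis window", and derives the 7-day SABA baseline in the same way. SAP 6.4.5 divides the summed hand-held FEV1 or PEF by the "Number of Days in the analysis window". SAP 6.4.3, which lies between them, divides night-time awakenings by "Days with assessments recorded in the eDiary during an analysis window".

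**Baselines.** SAP 4.2 gives the general rule: "The baseline for hand-held spirometry parameters and e-diary variables will be the average of the values over the 7 days preceding day of randomization". SAP 6.1 repeats it for spirometry and e-diary variables ("will be based on the daily average of the values over the 7 days preceding day of randomization"), and Protocol 9.6.1 agrees. SAP 6.4.5 departs from it twice. For the monthly averages it says "The baseline will be calculated based on the data from 28 days preceding day of randomization similarly". For the weekly averages it says "The baseline will be the summation of reported usage from 7 days preceding day of randomization".

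**Missing days.** Protocol 9.3.1 limits the analysis of all variables to observed data. SAP 4.3 restates that rule more narrowly: "For all safety variables, only the observed data from the patients will be used in the statistical analyses". The SAP's Introduction gives the SAP precedence where the two documents differ, and SAP section 15 declares no changes to the protocol's analyses.

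**The concern.** No passage says that a missed day is set to zero, but the two formulas have that effect. Zero litres is not a possible FEV1, and a blank diary day is not a day without rescue use. The reported window mean becomes the true mean multiplied by the fraction of days recorded, so change from baseline mixes adherence with lung function or rescue use.

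The bias can go either way. More missed days before randomization make SABA use appear to rise, and more missed days afterwards make it appear to fall. Equal missingness in both arms shrinks a true effect and adds noise. Unequal missingness after randomization becomes a false treatment difference.

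The two baselines in 6.4.5 are a separate fault. The hand-held spirometer is not dispensed until Visit S2, so many patients cannot have 28 days of pre-randomization data. A 7-day sum is also not on the same scale as the weekly average it is subtracted from. Both shift the two arms alike, so they distort within-arm changes and do not by themselves create a difference between arms.

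**Working it through.** The plan states no figure for this point, so there is none to reproduce. The check is arithmetic on the formulas, followed by a simulation of the between-arm consequences.

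**Inputs from the documents**
- Protocol 4.3: randomization requires acceptable data on at least 4 of the 7 preceding days.
- Protocol 3.1: screening and run-in last 4 to 5 weeks (28 to 35 days). The spirometer and e-diary are dispensed at S2, 14 ± 3 days after S1 (day 11 to 17). Run-in lasts at least 14 days and can be extended by up to 14 days.
- Planned size: 62 per arm.

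**Inputs assumed (not in the documents)**
- True FEV1 of 1.9 L.
- True SABA use of 4 puffs/day (range 2 to 6).

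**1. Denominator.** Value as written = true daily mean × (days recorded / days in window), if recorded days are representative.
- At the entry minimum: 4/7 = 0.571, so the average is 57% of the truth. This is the floor for the baseline week, not a prediction for the treatment period.
- SABA, unchanged true use of 4 puffs/day, 4/7 recorded at baseline and complete follow-up: 4 − 4 × 4/7 = +1.71 puffs/day. At 2 puffs/day it is 2 × 3/7 = 0.86, and at 6 puffs/day 6 × 3/7 = 2.57. The reverse pattern gives −1.71 at 4 puffs/day.
- With recorded days as denominator, a stable patient shows a change of 0 however many days are missed.

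**2. 28-day baseline.** Possible device days before randomization:
- Minimum 14; maximum without the extension 35 − 11 = 24. Divided by 28, the baseline is 14/28 = 50% to 24/28 = 86% of the truth.
- False within-arm gain at full adherence: 1.9 × (1 − 24/28) = 0.27 L to 1.9 × (1 − 14/28) = 0.95 L.
- With the extension up to 49 − 11 = 38 days are available, so some patients can fill all 28.

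**3. Weekly sum baseline.**
- Seven days recorded: 7 × 1.9 = 13.3 L, so the change is 1.9 − 13.3 = −11.4 L.
- Four days recorded: 4 × 1.9 = 7.6 L, so the change is 1.9 − 7.6 = −5.7 L.

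**4. Simulation of hand-held FEV1.** ANCOVA on change adjusted for baseline, 62 per arm, 4,000 trials. Assumptions: baseline mean 1.9 L, SD 0.5 L; SD of change 0.25 L; adherence beta-distributed with mean 0.85 and SD 0.12, with the same patient propensity before and after randomization; at least 4 of 7 baseline days; 28-day post-baseline window. Adherence gaps apply only after randomization. Unless stated, the baseline covers 7 days and is divided by 7.

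| Scenario | Estimated effect | Residual SD | Rejection, two-sided 5% |
|---|---|---|---|
| Recorded-day averages, true effect 0.10 L | 0.10 L | 0.25 L | about 60% |
| All-day averages, 85% adherence in both arms, true effect 0.10 L | 0.085 L | 0.33 L | about 30% |
| Same, 95% adherence (SD 0.05) | 0.95 × 0.10 = 0.095 L | 0.29 L | about 45% |
| Active arm 5 points lower, no true effect | about −0.10 L | – | 35–39% |
| 2-point gap, no true effect | 0.02 × 1.9 = 0.04 L | – | 10–11% |
| Active arm 5 points lower, true effect 0.10 L | about −0.015 L | – | – |

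A gap with the active arm higher gives a false difference of similar size in the other direction. With the 28-day baseline (14 to 24 device days, 85% adherence) the placebo arm shows a false gain of 0.52 L, and residual SD is 0.37 L against 0.33 L with the 7-day baseline.

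**The case against.** The strongest reply is that this is loose drafting, not a chosen method. SAP 4.2 speaks of an average of the values, which most readers take to mean recorded values. Protocol 9.3.1 covers all variables, and SAP 4.3 is silent on efficacy and does not contradict it. Section 15 declares no departures from the protocol. The weekly sum looks carried over from the ICS derivation in SAP 6.4.4, where usage can sensibly be summed, and a change of −11.4 L would be noticed in output review. These points make the intent plausible. They do not change the formulas, and the explicit recorded-day denominator in 6.4.3 counts against reading the other two the same way. A SAP should not leave the choice to the programmer.

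A second objection is that multiplying a baseline covariate by 7 leaves the treatment estimate and residual SD unchanged. That is right for a sum compared with sum/7. It fails against the recorded-day average, because the sum still carries the missed days. With the post-baseline average already corrected, the sum baseline raises residual SD from 0.25 to 0.37 L in the same simulation.

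Third, the simulated figures depend on assumed adherence. This stands: at 95% adherence or a 2-point gap the harm is much smaller, as the table shows. No document predicts a gap, the trial is double-blind, and randomization balances pre-randomization missingness in expectation. The recorded-day average also relies on recorded days being representative.

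Finally, the reach is limited. Primary LoAC is determined by the investigator, key secondary FEV1 is measured on site, and all secondaries are hypothesis-generating.

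**Conclusion.** The concern holds. Followed as written, SAP 6.3.4 and 6.4.5 give wrong window averages whenever a day is missed, and both baselines in 6.4.5 conflict with the SAP's own general rule. The ratios come from the documents: 57% of the true mean at the entry minimum, and 50% to 86% for the 28-day baseline without the extension.

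The losses for FEV1 rest on assumed level, spread and adherence, and are best read as a range. A test with about 60% power falls to about 30% at 85% adherence or about 45% at 95%. With no true effect, an adherence gap of 2 to 5 points rejects in roughly 10% to 39% of trials. The trial is not powered on this endpoint, so the power figures show loss of precision only.

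Among the key secondaries only SABA use is affected; hand-held FEV1/PEF is another secondary endpoint. This should be corrected before analysis, but it does not threaten the primary result.

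**What to change.** In SAP 6.3.4 and 6.4.5, make the denominator the number of days in the window with a recorded, acceptable value, for baseline and post-baseline windows alike, as SAP 6.4.3 already does. In SAP 6.4.5, use the 7-day average baseline of SAP 4.2 for both the monthly and the weekly hand-held analyses, in place of the 28-day baseline and the 7-day sum. The cost is SAP wording and programming; no new data are needed.
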